### A2. Specific Aims and Hypotheses

In the planned trial, 90 individuals with heterogeneous chronic pain who are at risk for opioid misuse will be randomly assigned to telehealth-delivered CT, MM, or AS. Mechanisms and outcomes will be assessed with actigraphy, twice daily EMA, and weekly telephone interviews during baseline, treatment, and for 4-weeks post-treatment. Mechanisms of longer-term maintenance of gains will be evaluated at 3- and 6-month follow-up. Given past research showing equivalent efficacy for active treatments, we expect no significant group level outcome differences between conditions. However, we do expect *individual* variability in treatment response and maintenance of gains that will allow us to examine mechanisms of change. This study will address two aims.

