## **D5. Participants**

We propose to enroll 90 participants. The anticipated lost to follow-up rate for this study is 20% of the total enrollment number, or 18 participants. We anticipate that with 90 participants enrolled (although we may elect to continue to enroll beyond this if we have the resources to do so, as this would provide even more power for the planned analyses) and a 20% attrition rate, we will have complete data for 72 of our participants; the primary analyses are to be conducted with the intent to treat sample.

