### **ActiGraphs**

Activity levels and sleep will also be measured during these three time periods using the ActiGraph wGT3X-BT, which uses triaxial accelerometry that has been shown to be a valid measure of daily physical activity in people with chronic pain, and provides a more valid and reliable assessment of activity level than self-report methods. The ActiGraph will be worn all day (except when the participant is showering, swimming, etc.), including during sleep. The participant would wear the ActiGraph like a wrist watch on their non-dominant arm. There is no risk of electric shock with this device.

Research staff will provide the participant with verbal instructions on the use and care of the ActiGraph during the technology training session. These instructions will also be mailed/mailed to the participant so they can refer to them in the future.

ActiGraphs will be mailed out to all participants in a cohort about one week prior to the beginning of the 2-Week Baseline Monitoring Period to minimize the risk of participants losing the ActiGraph. ActiGraphs will only be mailed if the participant has completed all of the required baseline procedures that are scheduled to occur before the beginning of Baseline Monitoring (including the Baseline Assessment, Pre-Treatment Extended Assessment, Re-Assessment of Eligibility, and Technology Training). Participants will also be instructed to fully charge the ActiGraph using the provided charging cables before first use, and as needed throughout (i.e., when the monitor light begins to flash red – typically after approximately 1-week of consistent wear-time).

The participant will be instructed to send back the ActiGraph in a provided self-addressed stamped envelope at the end of the 4-Week Post-Treatment Monitoring Period. Research staff will download all data collected by the ActiGraph and link it to the participant's other data via their participant identification number. Data may be downloaded directly from the ActiGraph only with the assistance of ActiLife software that is unavailable to the general population. That is, participants will NOT have the ability to download the data from the device itself (e.g., onto their personal computer). The data will be stored on a secure server in de-identified form indefinitely.

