#### **D6k. Randomization**

We will begin randomizing participants no sooner than six days after the start of the 2-Week Baseline Monitoring Period and continue to randomize until the day before the first treatment group starts. All participants in the current cohort will be reviewed to see if they completed all required baseline procedures and are thus eligible for randomization. The required baseline procedures are as follows:

1. Provided Baseline data and Demographics;
2. Completed Pre-Treatment Assessment;
3. Participated in technology training session and verbally agreed they are comfortable with all study software and with participating in group sessions using the videoconferencing software;
4. Completed re-assessment of eligibility;
5. Completed at least 7/14 EMA surveys during Week 1 of the Baseline Monitoring Period.

All participants need to complete the above required baseline procedures before they will be randomized; however, exceptions to meeting all randomization criteria may be given by researchers on a case-by-case basis should there be any extenuating circumstances that prevent the participant from meeting all randomization criteria. For example, a participant could have trouble accessing or completing EMAs not due to lack of participant effort. Participants who do not meet the EMA completion criterion above may be offered the opportunity to be contacted in the future should the criterion be revised. At that point, they would be re-screened for eligibility and will re-complete any Baseline procedures that are needed. If the Baseline procedures are completed the subsequent time around, then the participant will be eligible for randomization.

Participants who are not randomized will be asked to mail back any ActiGraphs still in their possession. Randomization will occur in stratified blocks to ensure that participants with each sex and baseline MME units (average daily in the past week, assessed at Re-Assessment of Eligibility; 20-49 or >49 MMEs) have an equal chance of being randomized to one of the three conditions. Stratification will assure that the treatment groups are balanced regarding each stratification variable, so that the estimated effect of the treatment is not biased due to differences in distribution of sex or opioid use. The randomization procedures will also increase balance of treatment group sizes within each cohort.

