#### **D6l. Treatment Scheduling**

Cohorts of study treatment groups will be offered 3-5 times per year.

Trained clinicians will commit to offering at least three groups per year: one of each treatment type. This will reduce the potential for therapist bias on the outcomes.

An unblinded staff member will maintain lists of group assignments and coordinate the scheduling of sessions. Staff will provide clinicians with a list of participants who were assigned to each class.

Treatment reminders will be provided for each session using the participant's preferred method of communication. If a participant misses a session, the therapist or another staff member may contact the participant about the missed session. If the therapist or other staff member is not able to get a hold of the participant, additional follow-up may be conducted by research staff.

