**Table 3. Primary, Secondary, Co-Variate, and Mechanism Variables**

Variable Type	Domain	Measure (# items EMA, extended, weekly)
Primary Outcome	Morphine Milligram Equivalents (MMEs); average daily dose in past week	Self-reported opioid medication use (questionnaire, extended, and weekly)
Primary Mechanisms and Moderators	Cognitive Content Cognitive Process Activity Level Average Pain Intensity Depression Anxiety	Pain Catastrophizing – Items from Pain Appraisal Scale (3, 5, 5), Coping Strategy Questionnaire (CSQ) (0, 2, 2) Pain-Related Cognitive Process Questionnaire (PCPQ) Non-Judgment Scale (2, 6, 6) Actigraphy, Godin Leisure-Time Exercise Questionnaire (3, 3, 0), Hours spent sitting without exercising (EMA only) Numerical Rating Scale (NRS), 0-10 (1, 1, 1) PROMIS-29 Depression (0, 4, 4) PROMIS-29 Anxiety (0, 4, 4)
Secondary Outcomes	Mood Physical Function Sleep Quality Medication Use Cannabis Use Medication Use Attitudes  Post-Traumatic Stress Disorder Pain Interference	Positive and Negative Affect Schedule (PANAS) (2, 10, 0) PROMIS-29 Physical Function (4 items ext. only) Actigraphy, PROMIS-29 Sleep Disturbance (4 items ext. only) Medication Use Questionnaire (Extended only) Investigator-developed items on cannabis use (3 items ext. only) Survey of Pain Attitudes (SOPA) Medication Beliefs Sub-Scale (6 items ext. only), Pain Medication Questionnaire (PMQ) (26 items Baseline only) PTSD Checklist – Civilian Version (PCL-C) (0, 17, 0) PROMIS Pain Interference (5, 5, 0)
Secondary Mechanisms	Pain Self-Efficacy Patient Engagement Therapeutic Alliance Group Cohesion  Skills Engagement	UW Pain-Related Self-Efficacy Scale (3, 6, 0) Clinician reported patient engagement (5 items rated by clinician) Working Alliance Inventory (WAI) (12 items EMA only) Group Climate Questionnaire (GCQ-S) Engagement Scale (5 items EMA only) Duration and number of times practicing skills (EMA), number of days and duration of time practicing skills (Extended)

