**Table 4. Study Assessment Schedule**

Measures	EMA	Baseline	Pre-Treatment	Weekly Phone	During Treatment	Post-Treatment	3-Month	6-Month
Demographic Information		X						
Pain and Treatment History		X						
Start Back Tool		X						
Pain Medication Questionnaire (PMQ)		X						
Roland Morris Disability Questionnaire SF (RMDQ)		X						
PROMIS Pain Interference	X		X			X	X	X
Pain Appraisal Scale (PAS)	X		X	X		X	X	X
2-item Catastrophizing Scale from the Coping Strategy Questionnaire (CSQ)			X	X		X	X	X
Pain-Related Cognitive Process Questionnaire (PCPQ) Non-Judgment Scale	X		X	X		X	X	X
Godin Leisure-Time Exercise Questionnaire	X		X			X	X	X
Hours Spent Sitting w/o Exercising	X							
Pain Intensity NRS	X	X	X	X		X	X	X
Positive and Negative Affect Schedule (PANAS)	X		X			X	X	X
PROMIS-29 Sleep Disturbance			X			X	X	X
PROMIS-29 Physical Function			X			X	X	X
PROMIS-29 Depression			X	X		X	X	X
PROMIS-29 Anxiety			X	X		X	X	X
PTSD Checklist (PCL-C)			X			X	X	X
Medication & Cannabis Use			X	X		X	X	X
UW Pain-Related Self-Efficacy Scale	X		X			X	X	X
Participant Engagement					X a			
Working Alliance Inventory (WAI)	X b							
Group Climate Questionnaire (GCQ-S)	X b							
Duration and Times Practicing Skills	X					X	X	X
Sleep/Wake Times	X							
Health Care Utilization			X			X	X	X
Pleasant Events Schedule SF			X			X	X	X
Behavioral Activation for Depression Scale (BADS)			X			X	X	X
Global Quality of Life			X			X	X	X
Employment Status	X	X				X	X	X
Weight	X	X				X	X	X
Mindful Awareness and Attention Scale (MAAS)			X			X	X	X
Pain Resilience Scale			X			X	X	X
Pain-Related Cognitive Process Questionnaire (PCPQ) – Full			X			X	X	X
Control, Harm, Disability, and Medication Scales from the Survey of Pain Attitudes (SOPA)			X			X	X	X
PROMIS Cognitive Function Abilities			X			X	X	X
COVID-19 Impact Questions			X			X	X	X
Treatment Credibility and Expectancies	X c							
Patient Global Impression of Change (PGIC)						X	X	X
Patient Global Assessment of Treatment Satisfaction (PGATS)						X	X	X
Treatment Modality & Preferences						X		
Importance of Treatment Outcomes	X						X	
Qualitative Outcomes							X	
Optional Measures: Positive & Negative Response to Pain Scales, Future Self Questionnaire (FSQ), Valued Living Scale (VLS)			X			X	X	X

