Mechanisms of Psychosocial Treatments on Opioid Use in Chronic Pain

Statistical Analysis Plan

Plan Date: July 23, 2024

IRB Title: Mechanisms of Psychosocial Treatments on Opioid Use in Chronic Pain

Short Title: Living in Full Even (LIFE) with Pain Study

NCT Number: NCT03916276

Mechanisms of Psychosocial Treatments on Opioid Use in Chronic Pain

A randomized, 3-group, parallel-design, 90-subject clinical trial to test the mediators and moderators of cognitive therapy, mindfulness meditation, and activation skills on individuals with heterogeneous chronic pain conditions who are at risk for opioid misuse.

Study Chairman or Principal Investigator:

[name]., Professor and Vice Chair for Research, University of Washington Department of Rehabilitation Medicine

[name]., Senior Lecturer, University of Queensland School of Psychology

Supported by:

The National Center of Complementary and Integrative Health (NCCIH)
3R01AT008559-02S1

Study Intervention Provided by:

University of Washington

Estimates of treatment effects on outcomes. Descriptive statistics were computed for all outcomes. At each follow-up time (post-treatment, 3- and 6-month follow-ups), the average daily medication in MME was categorized into three groups (increase in dose, decrease in dose, or no change in dose from pre-treatment to follow-up), and then calculated the proportion of individuals at each follow-up time that increased dose, decreased dose, or reported no change. We also calculated the 95% confidence interval (CI) for those proportions using Jeffreys method (Bayesian). We then compared these proportions between treatment conditions using a Chi-square test. We also calculated the difference in proportions (and 95% CI's) between each pair of interventions.

We calculated the mean and standard deviation of the change from pre-treatment to follow-up of all of the secondary outcomes, as well as their effect sizes (Cohen's d's) and 95% CI. We compared the mean changes of the interventions via an ANOVA (change in outcome as response and intervention group as a factor), and calculated between groups effects and 95% CI. Effect sizes were calculated using the macro effect size in R software.

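### Secondary outcomes are compared on change with arm as the only factor. Adjusting for the pre-treatment value and strata would sharpen raw mean differences, by about 2–13% if the pre-post correlation is .5–.9 and the SDs are equal

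*SAP*

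**What the plan says.** The SAP gives the between-arm model for secondary outcomes in one sentence: "We compared the mean changes of the interventions via an ANOVA (change in outcome as response and intervention group as a factor". It then says that between-group effects were obtained with 95% CIs, without stating whether these are raw or standardised. The preceding sentence reports the changes as Cohen's d.

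Protocol D6k says "Randomization will occur in stratified blocks to ensure that participants with each sex and baseline MME units" are equally likely to receive each arm, with MME bands of 20–49 and >49. Neither document carries these strata into the secondary-outcome model. Section D6p speaks of covariates to be controlled for if needed. Section D6n, after mentioning comparisons of dropout between arms, adds as covariates whatever variables are found to separate the groups. Neither provision commits to the pre-treatment value or the strata.

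In Table 3 and "Table 4. Study Assessment Schedule", six continuous secondary scores have a value at pre-treatment, post-treatment, 3 months and 6 months: PANAS, PROMIS-29 Physical Function, PROMIS-29 Sleep Disturbance, SOPA medication beliefs, PCL-C and PROMIS Pain Interference. Two other measures fall outside the point. The medication questionnaire is listed as "Pain Medication Questionnaire (PMQ) (26 items Baseline only", so it has no change score. The ActiGraph is sent back "at the end of the 4-Week Post-Treatment Monitoring Period", so there is no 3- or 6-month actigraphy.

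**The concern.** A change score already requires the pre-treatment value, but it fixes the slope of follow-up on pre-treatment at 1. The data would normally choose a slope of r times the ratio of follow-up to pre-treatment SD. Where that slope is not 1, the change score carries noise that a fitted slope removes.

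Precision matters here because the protocol (A2) says "we expect no significant group level outcome differences between conditions". If no difference is expected, the informative result is how large a difference the interval excludes. Section D5 anticipates that "we will have complete data for 72 of our participants", so the pairwise intervals will be wide.

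The strata raise a related point. If they predict follow-up given the pre-treatment value and are left out of the model, the reported SE takes no credit for the balance that stratified randomisation created, and it is then too large.

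**Working it through.** **Step 1: the stated figure.** 90 × (1 − 0.20) = 72, as in D5. Over three equal arms, 72 / 3 = 24 per arm.

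**Step 2: what is not given.** The documents state no pre-post correlation r and no SD for any secondary outcome. Assumed: r = .5 to .9, with equal SDs first and unequal SDs in Step 5.

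**Step 3: closed form, equal SDs, SD units.** Half-width of the 95% CI for a pairwise raw difference = t × √(2V/24).

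- Planned: V = 2(1 − r), error df = 72 − 3 = 69, t = 1.9949.
- Adjusted for pre-treatment value, sex and MME band: V = 1 − r², error df = 72 − 6 = 66, t = 1.9966.

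| r | planned | adjusted | narrower by |
|---|---|---|---|
| .5 | 1.9949 × √(2 × 1.00/24) = 0.576 | 1.9966 × √(2 × 0.75/24) = 0.499 | 13% |
| .7 | 1.9949 × √(2 × 0.60/24) = 0.446 | 1.9966 × √(2 × 0.51/24) = 0.412 | 8% |
| .9 | 1.9949 × √(2 × 0.20/24) = 0.258 | 1.9966 × √(2 × 0.19/24) = 0.251 | 2.5% |

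**Step 4: simulation, to allow for chance imbalance.** Set-up: 90 randomised in permuted blocks within sex × MME band, 72 analysed at random, strata not prognostic.

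- Mean narrowing from the pre-treatment value alone is 12.7%, 7.2% and 1.7% at r = .5, .7 and .9.
- With the strata terms added it is 12.4%, 6.8% and 1.3%.
- The strata terms therefore cost about 0.4% of width with 72 analysed, and 0.06% with all 90 analysed.
- In a separate simulation that randomised 72 directly, the adjusted interval was the narrower one in 99.5%, 95% and 65% of trials.

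**Step 5: unequal SDs.** Let k be the follow-up SD divided by the pre-treatment SD. In large samples the width ratio is √[(1 − r²)k² / (1 + k² − 2rk)].

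- k = 0.8: r = .5 gives √(0.48/0.84) = 0.756, 24% narrower. r = .7 gives 21% and r = .9 gives 22%.
- k = 1.25: r = .5 gives √(1.172/1.3125) = 0.945, 5.5% narrower. r = .7 gives 1.0% and r = .9 gives 2.5%.
- The gain vanishes where rk = 1, for example r = .8 with k = 1.25.

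**Step 6: Cohen's d.** Dividing the planned difference by the SD of change cancels V. The half-width near zero effect is 1.9949 × √(2/24) = 0.576 at any r. Dividing the adjusted difference by its own residual SD gives 1.9966 × √(2/24) = 0.576. Nothing is gained on that scale.

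**Step 7: strata and the reported SE.** Take r = .5, two 50/50 strata factors, exact balance, and let each factor shift follow-up by d SD.

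- Shift in follow-up only: the strata add d²/2 to a change variance of 1, so the planned SE is overstated by √(1 + d²/2) − 1. At d = 0.3 this is 2.2%, and at d = 0.5 it is 6.1%.
- Same shift in both scores: it cancels in the change, and the planned ANOVA's overstatement is zero.

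The documents do not say which case is nearer.

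**The case against.** The case for leaving the plan alone is respectable. The change-score ANOVA is simple and valid. These are secondary outcomes in a trial whose aims concern moderators and mediators of opioid use, and no conclusion has been shown to change. At r = .9 with equal SDs the gain is about 2%, and the adjusted interval is wider in roughly a third of trials. The protocol does leave room for covariates. Six scores × three times × three pairs is 54 further intervals, and since the SAP is in the past tense they may form a second set of results produced after the fact. All of this stands as a limit on the stakes. It does not remove the gain at lower correlations, and a provision that depends on need or on observed differences is not a pre-specified adjustment.

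A reader might infer more than the documents support:

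- That the planned comparison is biased. Randomisation makes it unbiased with or without covariates.
- That 2–13% applies to this trial as it stands. The range needs both r = .5–.9 and equal SDs, and neither is documented.
- That every planned interval would shrink. The SAP leaves the scale of its between-group effects open, and the gain is confined to raw differences.
- That the planned SEs are about 6% too large. That needs strata which shift follow-up by 0.5 SD and leave the pre-treatment score untouched.

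A separate limit is that treatment is given in groups (D6l: "Cohorts of study treatment groups will be offered 3-5 times per year") and neither model allows for clustering by group. The comparison between the models is little affected. In simulation at r = .5 with an assumed ICC of .02–.05, the true SE of the adjusted estimate was .865 to .882 times that of the planned one.

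**Conclusion.** The point holds as a modest, nearly free gain in precision. The SAP's model omits a pre-treatment value and strata that the trial already collects. How much narrower the raw pairwise intervals become depends on unstated quantities: about 2–13% for r = .5–.9 with equal SDs at 24 per arm, more if scores are less variable at follow-up, less if they are more variable. Almost all of the gain comes from the pre-treatment value. The strata terms cost under 0.5% if they are not prognostic. If they predict follow-up given the pre-treatment value, including them corrects reported SEs that are otherwise somewhat too large, by an amount that depends on whether they also shift the pre-treatment score. It is a change worth considering and not a fault that invalidates the analysis.

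**What to change.** For each of the six scores, at post-treatment, 3 months and 6 months, regress the follow-up value on arm + pre-treatment value + sex + MME stratum. Report adjusted raw pairwise mean differences with 95% CIs. Change may be kept as the response if preferred: with the pre-treatment value in the model, the arm effect and its SE are identical. State whether the SAP's between-group effects are raw or standardised.

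If the planned analyses have already been run, keep the ANOVA and report this model beside it, labelled as added after the SAP, so that neither result is selected over the other.

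The cost is 3 error df (69 to 66), one model line per score and one extra set of intervals. No new data are needed. There is little or no benefit if r is near .9 or above with equal SDs.

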## **Sample Size and Population**

We plan to enroll 90 participants with moderate to severe chronic pain who are also at risk for opioid misuse.

Enrolled participants who complete the required baseline components (baseline data and demographic questions, pre-treatment extended assessment period, technology training, pass the re-assessment of eligibility, and a minimum number of EMA surveys during one week of Baseline Monitoring (Days 1-7)) will be randomized to one of the three conditions.

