## D2. Study Timeline

We designed a four-year study plan and timeline for achieving short-term study objectives. There will be approximately 35 months available to enroll 90 participants. The anticipated lost to follow-up rate for this study is 20% of the total enrollment number, or 18 participants. We anticipate that with 90 participants enrolled (although we may elect to continue to enroll beyond this if we have the resources to do so, as this would provide even more power for the planned analyses) and a 20% attrition rate, we will have complete data for 72 of our participants; the primary analyses are to be conducted with the intent to treat sample.

Months 01-06 in Year 01 (Year 02 of the parent grant) will be spent finalizing internal operating procedures surrounding the study. Participant enrollment will require approximately 3 years (36 months; Month 07, Year 01 through Month 06, Year 04). Data collection and cleaning will be ongoing through Month 12, Year 04. Data analysis and dissemination will occur following data collection and cleaning. Drs. [name] and [name] will closely monitor study flow and will hold regular conference calls to coordinate study procedures. Both PIs will be directly involved with the details of the study at every level. Intra-site team meetings with staff and Co-Is will be conducted to ensure any issues will be addressed as they arise.

Milestone	Year 1*				Year 2*				Year 3*				Year 4*			
	1	2	3	4	1	2	3	4	1	2	3	4	1	2	3	4
Finalize administrative supplement protocol, data collection procedures, and obtain IRB approval	X	X														
Enroll 90 participants and execute study procedures			X	X	X	X	X	X	X	X	X	X	X	X	X	
Data analysis; evaluate benchmarks to determine whether to proceed to grant application for a larger study															X	X
Dissemination of study findings															X	X

\*Add one year for time corresponding to parent grant

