#### **D6m. Treatment**

Participants will attend eight 90-minute group treatment sessions scheduled on average twice per week for four weeks. In all three treatment conditions, group sessions will be conducted via the online, HIPAA-compliant Zoom videoconferencing platform (<https://zoom.us/>) with support from UW IT Services. Zoom videoconferences allow participants to see and hear each other, and also allows screen sharing, giving clinicians the opportunity to display visual information (e.g., PowerPoint slides) during the session. In the event that a participant cannot

access the videoconference during a specific session, we will provide workbooks to follow along with and to facilitate skills practice outside of sessions.

Participants may participate in Zoom sessions through a smart phone, tablet, laptop, or desktop computer. All participants will be provided instructions and training prior to their first scheduled session on how to log in, join the session, set up their video/audio components, and how to navigate the various menus/buttons within Zoom. Finally, participants are required to participate in sessions in a quiet, private location free from distractions to maximize treatment engagement and to protect the privacy and confidentiality of the sessions (e.g., their home or private office).

The group sessions will be conducted by PhD- or Masters-level clinicians with at least two years of clinical experience and who have undergone training that prepares clinicians to conduct each of the three treatment interventions in a group setting. The study clinicians will be trained and supervised by the investigators who have a great deal of experience in providing the study treatments. The clinicians will be provided with a detailed treatment manual and protocol outline, and Drs. [name] (CT intervention), [name] (MM intervention), or [name] (AS intervention) will provide regularly scheduled (weekly for the first two cohorts facilitated by any new study clinician; this may decrease to twice monthly once the study clinician has experience with the interventions and has demonstrated at least 90% treatment fidelity for the interventions provided) supervision for the study clinicians.

We will have a goal of having each group led by one or two clinicians allowing for groups to continue as scheduled in the event one of the clinicians is unable to attend a particular group.

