We applied this approach to the three active treatments in pilot data obtained in our RCT comparing CT, Hypnosis and Hypnotic-CT (within the subsample of participants who reported musculoskeletal pain who were prescribed opioids,  $N=18$ ) to examine the relative statistical power achieved in that sample to detect medium to large effects for the analyses planned for this supplemental project. In two PROCESS models testing if early change in pain intensity or depression were specific vs. shared mechanisms in accounting for late treatment change in opioid use, results showed: (1) a non-significant effect of condition on outcome (path *c*) as well as on both mechanisms (path *a*); and (2) a significant effect of both mechanisms on the outcome (path *b*;  $ps < .01$ ). Post-hoc correlations were then conducted for descriptive purposes. We found that early change in both pain intensity and depression were significantly associated with later change in opioid use across groups ( $rs = .58$  and  $.68$ , respectively); on the other hand, early change in outcome was not significantly associated with later change in mechanism. Taken together, these results (1) provide support for early change in pain intensity and depression as underlying later reductions in opioid use, and (2) are consistent with a shared mechanisms account for the role of early change in pain intensity and depression as mechanisms driving decreased opioid use across the treatments studied in this pilot data. The proposed sample size and procedures of the supplemental project will afford the capacity to test these associations more definitively.

Overall, our pilot data indicate that if changes in outcome and mechanisms in the supplemental project are medium to large in nature, then the sample size of  $N=90$  will be adequate to test the mediation hypotheses 2a and 2b. Support for Hypothesis 2a and the shared mechanisms conceptualization would be found in the instance of a non-significant effect

of condition on the mechanism variable, but significant ( $\alpha \leq .05$ ) effect of the mechanism on outcome collapsed across groups. Support for Hypothesis 2b on the other hand would be found in the instance of a significant effect of condition on the mechanism, with change in the mechanism differentially associated with change in outcome across treatment conditions.

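### Therapy is given in groups nested within arm, but the planned arm comparisons treat participants as independent; standard errors will be too small if members of a group have positively correlated outcomes

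*SAP*

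**What the plan says.** Delivery (Protocol D6m): "Participants will attend eight 90-minute group treatment sessions scheduled on average twice per week for four weeks". The same section aims for one or two clinicians per group. Scheduling (Protocol D6l): "Cohorts of study treatment groups will be offered 3-5 times per year". Clinicians commit to running at least one group of each treatment type a year. Group cohesion is listed as a secondary mechanism (Protocol Table 3), so the trial itself treats the group as possibly active.

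Analysis (SAP): mean changes in the secondary outcomes are compared between arms "via an ANOVA (change in outcome as response and intervention group as a factor". The proportions whose daily opioid dose rose, fell or stayed the same are compared by chi-square, with pairwise differences and 95% intervals.

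Analysis (Protocol D6s): Aim 2 uses PROCESS bootstrap models and examines the significance of each path. A non-significant effect of condition on the mechanism is one requirement for Hypothesis 2a (shared mechanism). For Hypothesis 2b (specific mechanism): "Support for Hypothesis 2b on the other hand would be found in the instance of a significant effect of condition on the mechanism". That sentence goes on to require also that the mechanism-outcome association differ between conditions.

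Neither document mentions a random effect, cluster-robust variance, cluster resampling, ICC or design effect for therapy group. For the ANOVA and chi-square the omission is plain from the SAP. For PROCESS it is inferred from silence.

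**The concern.** People who share the same eight sessions, clinicians and fellow members may come to resemble one another in outcome. Individual randomisation does not prevent this, because the resemblance arises afterwards. Having clinicians deliver all three treatments limits confounding of clinician with arm, but each therapy group still sits inside one arm. Variation between groups therefore adds to the variance of an arm mean, and an analysis of independent individuals leaves that part out.

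The place where this matters most is path a of Aim 2. An understated standard error there makes the non-significant result needed for Hypothesis 2a harder to obtain, and makes one of the two conditions for Hypothesis 2b easier to meet. The SAP's ANOVA, chi-square and pairwise intervals share the problem. The Aim 1 interaction tests are less affected, because the moderators vary between members of the same group.

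**Working it through.** **Inputs from the documents**
- Enrolment: "We plan to enroll 90 participants with moderate to severe chronic pain who are also at risk for opioid misuse" (Protocol, Sample Size and Population).
- Allocation: participants "have an equal chance of being randomized to one of the three conditions" (Protocol D6k), taken as 30 per arm.
- Attrition: "The anticipated lost to follow-up rate for this study is 20% of the total enrollment number, or 18 participants" (Protocol D2). 90 x 0.80 = 72, which reproduces the plan's number with complete data.
- Enrolment period: "There will be approximately 35 months available to enroll 90 participants" (Protocol D2).
- Cohorts: 3-5 a year (Protocol D6l).

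**Inputs that are assumed**
- One group per arm per cohort. The current text gives no group size.
- ICC between 0 and .15. The documents give none.

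**The plan's own figure.** Protocol D6s says N=90 is enough for medium to large effects. It states no power, numeric effect size or ICC, so there is no calculation to reproduce.

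**Group size**
- Cohorts: 35/12 x 3 = 8.75 and 35/12 x 5 = 14.6, so about 9-15.
- Groups: 9 x 3 = 27 to 15 x 3 = 45.
- Mean size m at N=90: 90/45 = 2.0 to 90/27 = 3.3. At 72 completers: 72/45 = 1.6 to 72/27 = 2.7.

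**Design effect at N=90.** DE = 1 + (m - 1) x ICC; true standard errors exceed the naive ones by a factor of about the square root of DE.

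| ICC | DE, m=2.0 | DE, m=3.33 | SE factor |
|---|---|---|---|
| .05 | 1.05 | 1.12 | 1.02-1.06 |
| .10 | 1.10 | 1.23 | 1.05-1.11 |
| .15 | 1.15 | 1.35 | 1.07-1.16 |

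**Type I error of the three-arm ANOVA at nominal 5%.** Simulated with no arm effect and groups nested in arm, 15 to 9 groups per arm:

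| ICC | N=90 | 72 completers |
|---|---|---|
| 0 | about 5.0% | about 5% |
| .02 | 5.1-5.7% | - |
| .05 | 5.8-6.8% | 5.5-6.4% |
| .10 | 6.7-8.6% | - |
| .15 | 7.6-11.1% | 6.7-9.5% |

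Repeat simulations agree to within about half a percentage point.

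**Related quantities, at ten groups of three per arm and ICC .05, .10, .15**
- Coverage of nominal 95% pairwise intervals: 93.8%, 92.6%, 91.4%.
- Type I error of the 3 x 3 chi-square: 5.8%, 6.4%, 7.9%.
- ANOVA with the group mean square as error and 3(J - 1) degrees of freedom, J being groups per arm: about 5% throughout.

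**Precision of an ICC estimate.** With k groups in total, SE is approximately the square root of 2(1 - ICC)^2 [1 + (m - 1)ICC]^2 / [m(m - 1)(k - 3)]. For ICC .05, m=3.33, k=27: 2 x 0.9025 x 1.247 / (3.33 x 2.33 x 24) = 0.0121, and the square root is .11. For m=2.0, k=45 it is .15. At 72 completers the range is .14-.22.

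**The case against.** The strongest case on the other side is about consequence and size, since the documents contain no group term anywhere.

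- **The ICC may be near zero.** A reader might infer that the intervals are too narrow as a matter of fact. The documents do not support that: they give no ICC, at zero the planned tests are correct, and at .02 the error is at most 5.7%. This stands, and the point is conditional for that reason.
- **Path a alone does not establish Hypothesis 2b.** A reader might infer that ignoring groups is enough to produce a finding of specific mechanisms. Protocol D6s also requires mechanism-outcome associations that differ by condition, a slope comparison on which grouping has less effect. This stands. One condition is biased, not the whole rule.
- **Arm differences are not the main question.** Protocol A2 expects none in outcome, and the ANOVA covers secondary outcomes. This lowers the stakes for the ANOVA, but path a still belongs to a primary-aim hypothesis.
- **An opposite bias exists.** Randomisation is stratified by sex and baseline opioid dose (Protocol D6k), yet the ANOVA includes neither, which makes it conservative. If the strata explained 10% of outcome variance (an assumption), simulated error at ICC .05 and N=90 would be 4.3-5.4%. The offset is real; its size is unknown.
- **The data cannot settle the ICC.** A standard error of .11 or more around a value of .05 is uninformative. This stands, but it does not justify fixing the ICC at zero.
- **Group size is inferred.** The documents do not say whether parent-study participants share the groups. Larger groups would worsen the problem: at five per group, error is 8.1% at ICC .05 and 11.9% at .10.

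**Conclusion.** The omission is real, and nothing else in the documents repairs it. Its effect is modest under the stated schedule: for ICCs of .05 to .15, a nominal 5% arm comparison runs at about 6% to 11% with 90 participants and somewhat lower with 72. This rests on a positive within-group correlation, one group per arm per cohort and 9-15 cohorts, and it does not count the offset from the omitted stratification factors. With that offset and a small ICC, the net direction is uncertain. The change is worth making because it touches one of the conditions that separate Hypotheses 2a and 2b. The documents do not support the stronger conclusions that the reported intervals are certainly wrong or that Aim 2 would be decided wrongly.

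**What to change.** - Fit the SAP arm comparisons of mean change and the Aim 2 path-a model with a random intercept for therapy group nested in arm, small-sample degrees of freedom, and sex and baseline opioid-dose stratum as covariates. State what is done if the estimated group variance is zero, since the model then reduces to one for independent participants.
- Replace the plain chi-square by a group-level permutation test or a cluster-adjusted test.
- Report the ICC with its confidence interval, which will be wide, and the actual group sizes.

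Cost: no new data. Group membership is on the assignment lists (Protocol D6l) and clinician rosters (Protocol D6m, Attendance Records). The SAP is dated July 2024 and written in the past tense, so this means re-running these analyses as well as changing the text. Intervals would be slightly wider.
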